12.2 Safety Endpoints

12.3 Laboratory Assessments

Laboratory measurements for blood chemistry, PSA, haematology, urinalysis, and will be performed according to the schedule of assessments ([Table 9-1](#)). Specific details not

mentioned in this section (including shipping requirements) are included in the laboratory manual.

All blood samples are to be collected after 8 hours fasting, after ECG and vital sign measurements.

12.3.1 Clinical Laboratory Tests

Blood Chemistry

Sodium, potassium, chloride, bicarbonate/CO₂, blood urea nitrogen, creatinine, fasting glucose, albumin, alkaline phosphatase, AST, ALT, prothrombin time/INR, total bilirubin, total protein, calcium, lipid panel (total cholesterol, LDL, HDL, triglycerides), and PSA will be measured.

Estimated glomerular filtration rate (eGFR) will be calculated based on Cockcroft-Gault formula:

$$eGFR = ((140 - \text{Age}) / (\text{SerumCreat})) * (\text{Weight} / 72)$$

Haematology

Haemoglobin, white blood cell (WBC) count with differentials (monocytes, eosinophils, basophils, neutrophils, lymphocytes) as an absolute value, red blood cell (RBC) count, and platelet count will be measured.

Due to the potential for dehydration to affect haematocrit, subjects should come fully hydrated during the trial when the haematocrit is tested to ensure reliable results.

Urinalysis

Specific gravity, pH, semi-quantitative “dipstick” evaluation of glucose, protein, bilirubin, ketones, leukocytes, and blood will be measured.

A microscopic examination including RBC and WBC will be performed only when dipstick evaluation is positive for WBC and/or blood or protein. A midstream urine sample (about 30 mL) will be obtained, in order to avoid contamination with epithelial cells and sediments, and allow proper assessments.

12.4 DEXA Scan

Bone density will be evaluated with standard procedure described in study imaging manual. All evaluations during the study for particular subject should, where possible, be performed on the same machine with particular attention to ensuring consistency in positioning patients.

To assess the spine, the subject will be in supine position with legs supported on a padded box to flatten the pelvis and lower (lumbar) spine. To assess the hip, the foot is placed in a brace that rotates the hip inward. The detector will be slowly passed over the area separately for spine and hip, generating images. The duration of examination will be up to 30 minutes. DEXA T Score will be calculated based on actual measured bone density value. Both values will be evaluated for safety.

EOT DEXA scan: If the subject is discontinued from the treatment early, DEXA will be performed only if they reached minimum Week 36 (Visit 4) active treatment period. In order to accommodate scheduling, EOT DEXA can be performed within 5 days before the EOT visit

12.5 Bone Turnover Markers

CTx1, osteocalcin, bone alkaline phosphatase, and PINP will be measured.

12.6 Hormonal Parameters

Total oestradiol. In order not to unblind treatment assignment, total oestradiol will be blinded.

12.7 Physical Examination

The following examinations will be performed:

1. Full evaluation and physical examination (general appearance, skin and body hair, neck [including thyroid]), eyes, ears, nose, throat, lungs, heart, abdomen, testicular examination, lymph nodes, lower extremities examination for oedema and basic nervous system evaluation)
2. Digital prostate examination. In a case an abnormality on prostate examination is detected, or subject develops significant worsening of obstructive urinary symptoms, it is recommended to have full urologic evaluation
3. Limited physical examination (cardiovascular system and lower extremities oedema) at all visits where a full physical examination is not scheduled. For lower extremities examination, subject will be sitting with their lower extremities in the dependent position. Lower extremities will be inspected and palpated to look for pitting oedema.

The lower extremities examination findings will be graded as per standard medical practice on a 5-point scale: 0 - no oedema; +1 - barely detectable 2 mm depression, immediate rebound; +2 - a 4 mm deep oedema, few seconds to rebound; +3 – 6 mm deep oedema, 10-12 seconds to rebound; or + 4 – 8 mm deep oedema, > 20 seconds to rebound; and recorded in the eCRF.

Information about the physical examination must be present in the source documentation at the study site. Significant findings that are present prior to the start of the study drug treatment must be included in the relevant medical history/current medical conditions.

12.8 Vital Signs

Blood pressure (SBP and DBP) and heart rate will be measured at all visits.

Details on body weight measurement are provided in [Section 11.3.2](#). Body weight taken at Baseline will be utilised for all PK calculations.

Blood pressure (SBP and DBP, see [Section 11.3.2](#)) and pulse rate will be assessed after the subject has rested quietly in the supine position for at least 5 minutes. Three consecutive

recordings will be taken and the average value will be noted in the eCRF. Blood pressure will be assessed using the same arm each time.

12.9 12-Lead ECG

The subject number and initials or date of birth, the date and actual time of the tracing, and the study code must appear on each page of the tracing. The ECGs should be performed at approximately the same time of day at each of the ECG assessments, after subject has been in supine position for 10 min. Tracings will be dated and signed by the person who interprets the ECG.

The eCRFs will contain:

1. Date and time of the ECG
2. Heart rate
3. PR interval
4. QT interval (QT_{cF})
5. QRS duration
6. RR interval

The overall interpretation will be collected with a yes/no statement to confirm if any clinically significant abnormalities are present, which need to be detailed further and reported as AE/SAE if appropriate. Original ECG tracings, appropriately signed, will be archived at the study site.

12.10 24/7 Medical Emergency Coverage

In a study related emergency situation, when assigned Medical Monitors for a study cannot be reached by a caller, an on-call Physician can be reached 24 hours per day, 7 days per week via an ICON Call Centre:

■ [REDACTED]

(Chargeable telephone number allowing a global reach from both landlines and mobile phones)

- <https://icophone.iconplc.com>

On this internet page, a list of country-specific toll-free telephone numbers is provided. It should be noted that not all countries globally have access to toll-free numbers as indicated on the “24/7 Medical Helpdesk” index. Countries without toll-free numbers need to dial the chargeable number as indicated above. Furthermore, toll-free numbers are not available from mobile phones.

13 STATISTICAL EVALUATION

13.1 Sample Size and Power

Primary Statistical Hypothesis: The percentage decrease from Baseline in lumbar bone mineral density measured in g/cm² by DEXA within a dose group is greater than [REDACTED]

H0: ≤ 3%

H1: > 3%

The null hypothesis will be rejected for a dose group and the endpoint considered met if the lower bound of the 2-sided 95% confidence interval (CI) for the percentage decrease from Baseline in lumbar spine is greater than [REDACTED].

Assuming a 2-sided test at 5% significant level and a standard deviation (SD) of 0.0439 g/cm², to achieve 90% power N=25 subjects in each dose group would be needed to detect a [REDACTED] decrease from Baseline in bone mineral density at 48 weeks.

Enrolment will continue until 30 subjects from each of the previous active treatment arms in Study MBGS205 have entered this study. Subjects previously treated with placebo will be enrolled until target subject population is met in all active arms.

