13.4 Endpoints

13.4.1 Primary Endpoint

The primary endpoint is percentage change in lumbar bone mineral density measured by DEXA (g/cm^2) from Baseline in Study MBGS205 to Week 48 in Study MBGS206 by dose group in subjects randomised to active treatment in Study MBGS205.

The primary endpoint will be assessed using the safety population.

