13.5.2 Analysis of Primary Endpoint

The percentage change from Baseline in lumbar bone mineral density measured in g/cm² by DEXA will be summarised by dose group and visit. A single sample 1-sided t-test conducted at the 2.5% significance level will be used to analyse percentage change from Baseline (MBGS205) at Week 48 (MBGS206) in each treatment arm to test the null hypothesis that the percentage decrease from Baseline is $\leq 3\%$. Only subjects that have a post-Baseline DEXA assessment in MBGS206 will be included in this analysis.

The primary analysis will be performed using the safety population.

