### 5 SAMPLE SIZE AND POWER

The statistical hypothesis is the percentage decrease from Baseline in MBGS205 to EOT in MBGS206 in lumbar bone mineral density measured in g/cm^2 by DEXA within a dose group is greater than ■■■:

H0: ■■■

H1: ■■■

The null hypothesis will be rejected for a dose group and the endpoint considered met if the lower bound of the 2-sided 95% confidence interval (CI) for the percentage decrease from Baseline in lumbar spine is greater than ■■■.

Assuming a 2-sided test at ■■■ significant level and a standard deviation (SD) of ■■■ g/cm^2, to achieve 90% power N=■■■ subjects in each dose group would be needed to detect a ■■■ decrease from Baseline in bone mineral density at 48 weeks.

Enrolment will continue until ■■■ subjects from each of the previous active treatment arms in Study MBGS205 have entered this study. Subjects previously treated with placebo will be enrolled until target subject population is met in all active arms.

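### The 90% power at N=25 rests on an SD in g/cm², but the primary test is on percentage change in lumbar BMD against a 3% null, and the visible text gives no conversion

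*Protocol*

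**What the plan says.** Protocol 13.1 states its hypothesis and its confidence-interval rule as a percentage decrease, with H0 at 3% or less. In the same section it sizes the study with an SD in absolute units: "a standard deviation (SD) of 0.0439 g/cm², to achieve 90% power N=25 subjects in each dose group would be needed".

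The endpoint and the test are both on the percentage scale. Protocol 13.4.1: "The primary endpoint is percentage change in lumbar bone mineral density measured by DEXA". Protocol 13.5.2: "A single sample 1-sided t-test conducted at the 2.5% significance level will be used to analyse percentage change from Baseline (MBGS205"), in order to "test the null hypothesis that the percentage decrease from Baseline is" 3% or less. SAP 8.6.2 plans the same test.

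SAP 5 repeats the pairing. It opens with "The statistical hypothesis is the percentage decrease from Baseline in MBGS205 to EOT in MBGS206 in lumbar bone mineral density" and then gives its SD in g/cm². The SD's value is blacked out there; its unit is not.

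The decrease to be detected is redacted in protocol 13.1, in the synopsis and in SAP 5. Protocol 7.2.1 says, unredacted, that the study is powered for a 3% decrease. No visible text gives a mean baseline lumbar BMD or an SD of percentage change.

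**The concern.** The power of a t-test on percentage change depends on the SD of percentage change. An SD in g/cm² supplies that only through the baseline level, which is not stated. The 90% therefore belongs to a calculation on another scale, and a reader cannot tell how far it carries over.

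This is the primary safety endpoint. If a dose group shows no significant bone loss beyond 3%, readers will use the stated power to judge how much loss the study could have missed. For that they need the detectable loss in the units of the test, measured from the 3% null.

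**Working it through.** **Inputs from the documents**

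- SD 0.0439 g/cm², N=25 per dose group, 90% power, 2-sided 5% (protocol 13.1).
- One-sample t-test, 1-sided 2.5%, on percentage change, null decrease at most 3% (protocol 13.5.2, SAP 8.6.2). The tail area is the same as for 2-sided 5%, so alpha is not in dispute.
- A 3% decrease as the effect powered for (protocol 7.2.1).

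**Assumed:** mean baseline lumbar BMD between 0.9 and 1.3 g/cm².

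**Step 1: reproduce the plan's figure.** For a one-sample t-test, power = P(T > t(0.975, n−1)), where T is noncentral t with n−1 degrees of freedom and noncentrality (difference/SD)·√n. With a difference of 0.03 g/cm²:

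- difference/SD = 0.03/0.0439 = 0.683; at n=25 the noncentrality is 0.683 × 5 = 3.42;
- power is 89.3% at n=24 and 90.6% at n=25.

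So N=25 is the smallest N that reaches 90% for 0.03 g/cm². Solving back from N=25 and exactly 90% power gives 0.676 SD, and 0.676 × 0.0439 = 0.0297 g/cm².

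**Step 2: compare with the 3% of protocol 7.2.1.** The printed figures match if 3% was taken as 0.03 g/cm². The two are equal at a baseline of 0.03/0.03 = 1.0 g/cm². Exactly 90% power for 3 percentage points occurs at 0.0297/0.03 = 0.99 g/cm².

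**Step 3: convert to the tested scale.** Approximate the SD of percentage change as 100 × 0.0439/baseline. This treats 0.0439 as the SD of change and ignores the spread of baseline between men. For N=25:

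| Assumed baseline (g/cm²) | SD (percentage points) | Power, true mean 3 points from the null | Distance from the null with 90% power (0.676 × SD) |
|---|---|---|---|
| 0.9 | 4.88 | 83.9% | 3.3 points |
| 1.0 | 4.39 | 90.6% | 3.0 points |
| 1.1 | 3.99 | 95.0% | 2.7 points |
| 1.2 | 3.66 | 97.6% | 2.5 points |
| 1.3 | 3.38 | 98.9% | 2.3 points |

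Power stays within 2 points of 90% only for baselines of about 0.957 to 1.027 g/cm².

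**Step 4: locate the null.** Step 3 measures distance from the tested value. Against the planned 3% null, 3 points away means a true decrease of 6%. A true decrease of 3% lies on the boundary of the null, where the rejection probability is the 1-sided alpha, 2.5%, at every baseline.

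**Dropout check.** 30 × (1 − 0.17) = 24.9, about 25, so the entrant target agrees with N=25.

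**The case against.** The strongest reply is that much rests on text that cannot be seen. The decrease to be detected is redacted where the sample size is stated, and a conversion between scales could sit under the redaction. The 0.03 g/cm² is solved back from N, SD and power, not read. With a difference of 2, 2.5 or 4 percentage points, the baseline giving 90% moves to 1.48, 1.19 or 0.74 g/cm². This stands, and it limits what can be said about the cause. It does not remove the mismatch, because the SD and its unit are legible in protocol 13.1 and the test is on percentage change.

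Protocol 13.1 also does not say what the SD is an SD of, and dividing by mean baseline is only an approximation. Both points stand, and both are reasons to state the SD of percentage change directly.

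A third reply is that all analyses are declared exploratory (protocol 13.5.1, SAP 8.6.1.1), confidence intervals will be reported, and neither N nor the test would change. That is fair. It makes this a correction to a statement, not to the design.

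A reader might infer that the study is underpowered, or that the 90% claim needs a baseline of almost exactly 1.0 g/cm². The documents support neither. On the approximation above, 0.99 g/cm² is a floor: power is at least 90% at any higher baseline. Protocol 7.1 says BMD rises with BMI, and exclusion criterion 6 removes men with a T-score below -2.0. Both point towards higher baselines and so towards power above 90% for that distance.

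**Conclusion.** The scale mismatch is established in protocol 13.1 and, by the unit of its SD, in SAP 5. The stated 90% is therefore not shown to apply to the primary test.

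Over the assumed baseline range of 0.9 to 1.3 g/cm², power for a true mean 3 percentage points from the null runs from 83.9% to 98.9%, about 6 points below to 9 points above the stated value. The upper part of that range is the more likely. These figures rest on the assumed baselines, on 0.0439 being the SD of change, and on the division by mean baseline.

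They do not describe power for a true 3% decrease, which is 2.5% against the 3% null whatever the baseline. That is a separate matter from the scale of the SD, but a restated power figure would mislead unless it names the true decrease assumed.

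That the sponsor treated 3% as 0.03 g/cm² is the reading that fits the printed numbers; the redactions prevent confirming it. A reader might also assume that the synopsis has the same fault. That cannot be shown, because both the SD and its unit are redacted there.

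**What to change.** In protocol 13.1 and SAP 5:

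1. Replace the SD in g/cm² with the SD of percentage change in lumbar BMD. Inform it from the MBGS205 Baseline and Week 24 DEXA scans pooled over arms, and add a caution that the Week 48 SD may differ. Protocol 7.1 itself calls 6 months too short to assess BMD.
2. State the assumed true percentage decrease and its distance from the 3% null.
3. Restate the power at N=25 for that decrease, or give the distance from the null detectable with 90% power, 0.676 × SD in percentage points.

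Keep 25 completers and 30 entrants per dose group, and keep the test. The cost is a few sentences and one summary of data from the parent study. The restated power may come out below or above 90%.

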13.2 Randomisation

Subjects that received active doses of BGS649 in Study MBGS205 will continue with the same dose in Study MBGS206. ICON Biostatistics will prepare the randomisation list, based on a randomisation scheme blocked by site. Each subject that received placebo in Study MBGS205 will be re-randomised to one of the 3 active doses defined in [Section 9.1](#) in a 1:1:1 ratio.

See [Section 10.2.4](#) for further details of the Randomisation procedures to be applied.

13.3 Analysis Sets

All safety endpoints will be analysed using the safety population. All efficacy endpoints will be analysed using the intention to treat (ITT) population.

Further safety and tolerability data will be analysed using the safety population.

PK data will be analysed using the PK population.

13.3.1 Intention to Treat

The ITT population includes all subjects who:

1. Are randomised, and
2. Receive at least 1 dose of study medication, and
3. Provide a Baseline efficacy value and at least 1 available evaluation of efficacy post-Baseline.

13.3.2 Safety Population

The safety population includes all subjects who received at least 1 administration of the study medication.

13.3.3 PK Population

For the summary of semen concentration of BGS649, all subjects who received at least 1 administration of the study medication and have at least 1 quantifiable concentration will be included in the PK population.

13.4 Endpoints

13.4.1 Primary Endpoint

The primary endpoint is percentage change in lumbar bone mineral density measured by DEXA (g/cm^2) from Baseline in Study MBGS205 to Week 48 in Study MBGS206 by dose group in subjects randomised to active treatment in Study MBGS205.

The primary endpoint will be assessed using the safety population.

13.4.2 Secondary Endpoints

13.4.2.1 Secondary Safety Endpoints

1. In subjects that were randomised to active treatment in Study MBGS205 by dose group:
 - Percentage change in hip bone mineral density measured by DEXA (g/cm^2) from Baseline in Study MBGS205 to Week 48 in Study MBGS206
 - Percentage change in bone turnover markers (C-terminal telopeptide [CTx1], osteocalcin, bone alkaline phosphatase, and procollagen type 1 N-propeptide [P1NP]) from Baseline in Study MBGS205 to Week 48 in Study MBGS206
 - Proportion of subjects with T-scores ≤ -2.5 at Week 48
 - Percentage change in bone density and bone biomarkers adjusted for vitamin D deficiency from Baseline in Study MBGS205 to Week 48 in Study MBGS206
 - Change of oestradiol (absolute and percentage) to Week 48
 - Proportion of subjects that overshoot testosterone (total testosterone above 1000 ng/dl [35 nmol/L], from first dose of study drug in Study MBGS205 until study completion)
 - Change in PSA from Baseline in Study MBGS205 to Week 48 in Study MBGS206
 - Change in haematocrit from Baseline in Study MBGS205 to Week 48 in Study MBGS206
 - Change in blood pressure (systolic and diastolic) Baseline in Study MBGS205 to Week 48 in Study MBGS206
 - Treatment emerged AE, SAE, and AESI (from first dose of study drug in Study MBGS205 until study completion)

- Relationship between change in bone mineral density from Baseline in Study MBGS205 to Week 48 in Study MBGS206 and absolute levels of oestradiol and total testosterone at Week 48 in MBGS206
2. In subjects that were randomised to placebo in Study MBGS205 by dose group:
- Percentage change in hip bone mineral density measured by DEXA (g/cm^2) from Baseline in Study MBGS206 to Week 48
 - Percentage change in bone turnover markers (CTx1, osteocalcin, bone alkaline phosphatase, and P1NP) from Baseline in Study MBGS206 to Week 48
 - Change of oestradiol (absolute and percentage) from Baseline in Study MBGS206 to Week 48
 - Proportion of subjects with T-scores ≤ -2.5 at Week 48 of Study MBGS206
 - Proportion of subjects that overshoot testosterone (total testosterone above 1000 ng/dl [35 nmol/L] from first dose of study drug in Study MBGS206 until study completion)
 - Change in PSA from Baseline in Study MBGS206 to Week 48
 - Change in haematocrit from Baseline in Study MBGS206 to Week 48
 - Change in blood pressure (systolic and diastolic) Baseline in Study MBGS206 to Week 48
 - Treatment emerged AE, SAE, and AESI (from first dose of study drug in Study MBGS206 until study completion).

13.4.2.2 Secondary Efficacy Endpoints

1. In subjects that were randomised to active treatment in Study MBGS205 by dose group:
- Percentage of subjects that have normalisation of total testosterone at Week 48 in Study MBGS206
 - Change in total and bioavailable testosterone from Baseline in Study MBGS205 to Week 48 in Study MBGS206
 - Change of LH and FSH from Baseline in Study MBGS205 to Week 48 in Study MBGS206
2. In subjects that were randomised to placebo in Study MBGS205 by dose group:
- Percentage of subjects that have normalisation of total testosterone at Week 48 of Study MBGS206
 - Change in total and bioavailable testosterone from Baseline to Week 48 in Study MBGS206
 - Change of LH and FSH from Baseline to Week 48 in Study MBGS206

13.4.2.3 Secondary Pharmacokinetic Endpoint

1. EOT plasma and semen concentration of BGS649 by dose group.

13.4.2.4 Exploratory Endpoints

1. In subjects that were randomised to active treatment in Study MBGS205:
 - Change in exploratory parameters from Baseline in Study MBGS205 to Week 48 in Study MBGS206 by dose group
 - Body composition (weight, BMI, waist and hip circumference, and parameters measured by bio-impedance)
 - Markers of cardiometabolic disease (blood pressure, lipid profile, HbA1c, glucose and insulin, hs-CRP, and HOMA-IR)
 - Physical activity, sleeping pattern, and strength (measured by wrist worn monitors and grip strength measurement)
 - Total and domain scores on PRO measures (Sexual function (IIEF, PROMIS SexSF), Energy/fatigue (BFI, PROMIS Fatigue), SF-36)
 - The relationship between changes in PROs and changes in body composition, physical activity, grip strength, and sleep
 - The relationship between changes in testosterone and changes in cardiometabolic parameters, body composition, physical activity, grip strength, sleep, and PROs.
2. In subjects that were randomised to placebo in Study MBGS205:
 - Change in exploratory parameters from Baseline in Study MBGS206 to Week 48 in Study MBGS206 by dose group
 - Body composition (weight, BMI, waist and hip circumference, and parameters measured by bio-impedance)
 - Markers of cardiometabolic disease (blood pressure, lipid profile, HbA1c, glucose and insulin, hs-CRP, and HOMA-IR)
 - Physical activity, sleeping pattern, and strength (measured by wrist worn monitors and grip strength measurement)
 - Total and domain scores on PRO measures (Sexual function (IIEF, PROMIS SexSF), Energy/fatigue (BFI, PROMIS Fatigue), SF-36)

